clinical evaluations, are undoubtedly higher when the symptom is evaluated by means of instrumental investigations (Tassorelli, et al 2008). According to the De Pauw study (De Paw, et al 2002), permanent dysphagia emerges in mildly impaired patients (EDSS 2-3), and becomes increasingly common as disability worsens, reaching a prevalence of 65% in the most severely disabled subjects (EDSS 8-9). Thus, diagnosis in the early stages may play an important role in limiting the consequences of this dysfunction. However, as patients themselves sometimes underestimate this symptom, diagnosis must be supported, as recently described in the literature, by functional tests and instrumental evaluations. A specific questionnaire (DYMUS: Dysphagia in Multiple Sclerosis) was published and validated for the assessment of dysphagia in MS. Its good internal consistency and the feasibility of administration has made it a reliable means to detect dysphagia in MS. In particular it consents to distinguish dysphagia to solids from dysphagia to liquids (Bergamaschi, et al.). 2008). However, a more detailed and objective evaluation is needed to investigate specific deficits and to plan appropriate rehabilitation; the Fiberoptic Endoscopy Evaluation of Swallowing (FEES) may be used for this purpose. In the 20 years since these initial reports, the FEES has become a validated technique for the evaluation of pharyngeal swallowing (Leder, et al 2008). The swallowing disturbances in MS are characterised by impairment of the oral and pharyngeal phases. Abraham et al. found impairment of the upper oesophageal sphincter in 100% of a small MS population (Abraham et al. 1997). Calcagno et al., using a mixed clinical and instrumental examination, subdivided their population into three groups according to the severity of dysphagia: severe, moderate and slight. Severe dysphagia group showed impairment of both oral and pharyngeal phases of swallowing, moderate dysphagia group showed motor impairment of the tongue, lips, velum or larynx, while the mild dysphagia group showed deficiency either of the velum or of the glottic closure. In the same paper, Calcagno et al. found that the compensatory strategies resolved dysphagia in about 94% of the cases (46 pts. Out of 49) (Calcagno et al., 2009). These strategies help to redirect and improve the food flow, avoiding aspiration and reducing the risk of pneumonia, but patients remain dysphagic and always need to perform compensatory strategies. (De Angelis et al 2008; Inagaki et al 2009,) As far as we know, this is the only study evaluating the rehabilitative approach, but it was not a control study. The role of food was highlighted in a recent paper showing that the main effect of food hardness is a delay in oral ejection time, which strongly delays total swallowing time, whereas pharyngeal bolus transit is dependent on its viscosity (Taniguchi et al 2008,). Recently, a pilot study (Frost, et al 2018) has shown as NMES could probably improve voice quality in MS patients: in fact, dysarthria has been proven to affect quality of life in MS patients (Piacentini, 2014).

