However, this type of treatment can be performed only in specialized centers and it is probably more invasive than NMES. In 2009, Bogaardt (Bogaardt et al 2009) conducted a Class IV trial with a sample of 25 patients with MS. The primary focus of the study was to examine the effects of NMES on pooling of saliva or liquid in the valleculae and pyriform sinuses. Six of the 25 patients had significant reduction in pooling of saliva in the pyriform sinuses, and 23 participants reported through a questionnaire that their swallowing had improved (Bogaardt, et al 2009). As far as we know, this is the unique paper focusing on the therapeutic effects of NMES in MS patients. Our research group recently published about the use of NMES in people with stroke and dysphagia. The methodology resulted safe with a good effectiveness in addition with traditional speech therapy. In fact, combined treatment seem to reduce the risk of penetration and aspiration in stroke dysphagic people. (Simonelli et al 2019).

The aim of the study is to determine whether NMES added benefit to a therapy program comprised of standard swallowing exercises in dysphagic pwMS

Materials and methods

The research plan will be implemented within a multi-center collaboration. Each of the 8 centers will recruit 17 inpatient and outpatient with a diagnosis of MS, according to revised McDonald criteria (Thompson et al 2018), with dysphagia. Each patient will be evaluated with a general and neurological evaluation scored according to the Expanded Disability Status Scale (EDSS) of Kurtzke and its functional systems.

Inclusion criteria will be:

- 1) Sex (both);
- 2) Age (older than 18)
- 3) Diagnosis: definite MS (Thompson et al 2018)
- 4) Stability: recruited subjects must be in a stable phase of the disease, without relapses which induce worsening > 1 point in the EDSS and with an EDSS <=8
- 5) ASHA<6 and DYMUS >2
- 6) Novelty: subjects should not have been trained with dysphagia program in the last 6 month
- 7) Mini-Mental State Examination: > 24;

Exclusion criteria will be:

- 1) dysphagia related to other diseases
- 2) presence of tracheal cannula
- 3) local or general contraindications to the use of equipment for electrical muscle stimulation of the neck
- 4) malignancies or acute inflammation in the anterior region of the neck.
- 5) lack of collaboration due to mental impairment

Baseline characteristics:

At T0, a clinical and instrumental examination will be suggested, concerning:

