Secondary outcome will be the differences obtained at T0-T2 and T0-T3 in the two groups in DYMUS scale, FESS/DOSS score, the MNA, the Swallowing Quality of life questionnaire, Penetration and Aspiration Score, the Visual Analogue Scale and the Pooling score.

Hypothesizing a response to treatment in the 30% of the SHAM group and in 60% of active NMSE a sample size of 56 subjects for each group provides a power of 0.9 and a significance level of 5%. ($h = 0.6128748$, $n = 55.94774$, sig.level = 0.05, power = 0.9, alternative = two.sided)

We estimate we could have a dropout of approximately 10-15%. In this light we decided to enrol 136 pwMS (17 for each center) Baseline characteristics and comparability of the two treatment groups will be assessed by the two samples t-test for continuous variables and by chi-square or Fisher's exact test for categorical variables. To address the first aim of the study, will be used analysis of covariance comparing changes in study outcomes from baseline to T2 adjusting for differences in baseline measures of swallow performance, diet and quality of life across the two treatment arms. To evaluate the differences intra-group, we will performed longitudinal analyses using general linear models for repeated measures of outcome data collected at baseline to T2 .

Italian MS Society Research Foundation is funding the study

(Grant No 2019/R –Multi/ 005)

References

Alali D1, Ballard K2, Bogaardt H Treatment Effects for Dysphagia in Adults with Multiple Sclerosis: A Systematic Review. *Dysphagia*. 2016 Oct;31(5):610-8. doi: 10.1007/s00455-016-9738-2. Epub 2016 Aug 4.

American Speech-Language Hearing Association. National Outcomes Measurements System (NOMS): Adult Speech-Language Pathology Training Manual. Rockville, Md: American Speech-Language Hearing Association; 1998

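### The primary ASHA ANCOVA names its covariates but leaves out baseline EDSS, which every patient has; adding it is a cheap, modest gain in precision

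*Protocol*

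**What the plan says.** The primary outcome is the mean difference in ASHA score between the active and sham arms. The statistical text at the end of the Briefly section plans an analysis of covariance of change from baseline to T2, "adjusting for differences in baseline measures of swallow performance, diet and quality of life across the two treatment arms". Under Primary Outcome, the protocol says more loosely that the groups will be compared after adjusting for baseline differences. It also plans baseline comparability tests but ties no action to their result.

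On EDSS, Materials and methods states: "Each patient will be evaluated with a general and neurological evaluation scored according to the Expanded Disability Status Scale". The inclusion criteria allow any EDSS up to 8 and set no lower limit. The Introduction reports that permanent dysphagia appears at EDSS 2-3 and "becomes increasingly common as disability worsens, reaching a prevalence of 65% in the most severely disabled subjects (EDSS 8-9").

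Under Rehabilitation treatment, allocation uses two blocked lists and is done by single centre. The text does not say what separates the two lists, and EDSS is not mentioned as a randomisation factor.

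**The concern.** The protocol does not leave the covariates open. It names three domains, and disability is not among them. EDSS is on file for every patient before treatment, spans a wide range, is not balanced by the stated randomisation, and is treated in the protocol's own background as related to dysphagia. If EDSS predicts the T2 ASHA score beyond what baseline swallowing, diet and quality of life already predict, leaving it out makes the primary estimate less precise than the collected data allow.

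The loose wording under Primary Outcome, together with baseline tests that lead nowhere, also leaves room to choose extra covariates after an imbalance has been seen. Fixing EDSS in advance removes that choice for the most obvious candidate.

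**Working it through.** **1. The plan's own figure.** The sample size assumes: "Hypothesizing a response to treatment in the 30% of the SHAM group and in 60% of active NMSE", with "sig.level = 0.05, power = 0.9, alternative = two.sided".

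- h = 2·asin(√0.60) − 2·asin(√0.30) = 0.6129
- n per arm = 2·((1.960 + 1.282)/0.6129)² = 55.95, so 56 per arm and 112 in total

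This reproduces. It is a calculation for two responder proportions and uses no covariates. The protocol gives no ASHA standard deviation and no power for the ANCOVA, so a change in precision can be expressed only as a ratio of standard errors.

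**2. Inputs for the effect of adding EDSS.**

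- Patients analysed: 112, the protocol's evaluable target.
- Existing model: intercept, arm and one term for each of the three named domains, so 5 parameters (assumption; the protocol does not list the individual measures). Adding EDSS makes 6.
- R²: the share of residual variance in T2 ASHA that EDSS explains after the listed covariates. The documents give no value. Assumed range: 0 to 10%.

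**3. Formula.** A further covariate multiplies the variance of the treatment difference by (1 − R²). It also costs a factor of about 1 + 1/(112 − 6 − 1) = 1 + 1/105 = 1.0095, because the covariate is by chance correlated with arm and uses a degree of freedom.

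SE ratio = √[(1 − R²) × 1.0095]

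| Assumed R² | Variance ratio | SE ratio | Change in SE |
|---|---|---|---|
| 0 | 1.0095 | 1.0048 | +0.5% |
| 0.02 | 0.9893 | 0.9947 | −0.5% |
| 0.05 | 0.9590 | 0.9793 | −2.1% |
| 0.10 | 0.9086 | 0.9532 | −4.7% |

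Break-even is at R² = 1 − 105/106 = 0.0094, just under 1%. At the top of the range, 112/0.9086 = 123.3, so the gain is worth about 11 patients. At R² = 0.05 it is 112/0.9590 = 116.8, about 5 patients.

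**4. What a chance imbalance does.** With 56 per arm, the chance difference between arms in a standardised covariate has standard deviation √(2/56) = 0.189. Take the part of EDSS not explained by the listed covariates and R² = 0.10. A one-standard-deviation imbalance then moves the estimate by 0.189 × √0.10 = 0.060 residual standard deviations. Its square, 0.0036, is 10% of the unadjusted sampling variance 2/56 = 0.0357. That is the same 10% that adjustment removes. The unadjusted standard error therefore already contains the effect of the imbalance.

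**The case against.** The strongest reply is that this is a preference. The final covariate list is often settled in the statistical analysis plan, which is not at hand, and an ANCOVA with baseline swallowing, diet and quality of life is already defensible. That stands as a limit on severity. It does not dispose of the point, because the protocol has stated a list and the suggestion is one specific change to it. The wording under Primary Outcome does not exclude EDSS, but it does not commit to it either.

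The second reply is that the cited background does not show what is needed. It concerns how common dysphagia is at different EDSS levels. Everyone enrolled is already dysphagic by ASHA and DYMUS, and the highest band quoted overlaps the entry range only at EDSS 8. No passage says that EDSS predicts change in ASHA given baseline swallowing. This also stands, and it is why the assumed range starts at zero.

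Three stronger readings are tempting and are not supported:

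- **A chance imbalance in disability would be mistaken for a treatment effect.** Under randomisation, leaving out a covariate neither biases the comparison nor inflates the type I error. Any imbalance that runs with baseline swallowing is partly corrected already.
- **Power would rise from 0.90.** That figure was stated for 30% versus 60% responders and is not the power of the ASHA mean comparison.
- **Inpatient or outpatient status should be added too.** The protocol recruits both ("Each of the 8 centers will recruit 17 inpatient and outpatient with a diagnosis of MS"). However, it does not list setting as a baseline variable or give evidence that it is prognostic, and setting may largely coincide with centre.

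Whether centre, the stated randomisation factor, belongs in the model is a separate question.

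**Conclusion.** The point holds as a minor efficiency recommendation. The named covariates omit a baseline measure that is collected in everyone, varies widely and is linked to dysphagia by the protocol itself. Under an assumed 0 to 10% of residual variance explained, the standard error of the primary difference changes by between about +0.5% and about −5%, and the gain turns positive once EDSS explains about 1%. The range rests on three assumptions: the R² values, 112 patients analysed, and one model term per named domain. A reader might infer that the primary result would be biased or its error rate wrong without EDSS; the documents do not support that.

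**What to change.** In the analysis paragraph, add baseline EDSS, entered as a score, to the fixed covariates of the primary ASHA ANCOVA and of the secondary between-arm models. State that it is included whatever the baseline comparability tests show. The cost is a few words of text, one model term and one degree of freedom, with no new data. The worst case is a standard error about 0.5% larger. The randomisation and the sample size need no change.

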- the Swal-QOL. This is a 44-items questionnaire is a highly valid instrument for evaluating and has a very reliable shorten reproducibility (Ginocchio D et al 2016). Its 11 subscales represents the different aspects of quality of life. The minimum and maximum score per subscale ranges from 0 to 100, indicating extremely impaired quality of life versus no impairment experienced by the individual;

- Visual Analogue Scale (VAS) for dysphagia: self-assessment of dysphagia severity will be rated from 0 (none) to 10 (worst imaginable) scale. Respondents will be classified as having no dysphagia (score 0), mild dysphagia (scores 1-4), moderate dysphagia (scores 5-6) and severe dysphagia (scores 7-10);
- the meal time.
- CGI (Clinical Global Impression Scale) scale for evaluating clinical changes after treatment (Busner et al 2007)

Two Speech Language Pathologists (SLPs) trained in dysphagia management will be involved: one, as evaluating speech therapist, will be blind on the NMES treatment and the other one as a treating speech therapist.

As far as the dysphagia concerned, patients will be considered dysphagic according to ASHA (score<6) and DYMUS (score >2).

The NICE guidelines (NICE 2014) identified from the literature a number of possible adverse events for NMES, which they classified under Safety section.

Those deemed likely were burning sensation, skin irritation or soreness beneath the electrodes and coughing or expectoration, neck or jaw pain and increasing severity of dysphagia. Incidences of these events were recorded during the NMES therapy. The therapists who delivered the NMES therapy were also asked to record any other adverse reactions. In addition, therapists were asked to record whether the adverse reaction was resolved by repositioning the electrodes.

Finally, the speech and language therapists were asked to note whether there was any change in the quality of the voice as a result of the NMES, as previous research has shown (Frost, 2018).

The training will consist of 16 sessions. After 8 (T1) every patient will be examined using: ASHA scale; VAS for dysphagia and meal time. After 16 (T2) sessions, every patient will be examined with both clinical and instrumental examinations; after 12 weeks (T3) from the end of treatment every patient will undergo clinical evaluations. At T3 the CGI will also be submitted to the pwSM caregivers

Rehabilitation treatment

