In the present study, VitalStim equipment will be used (VitalStim Therapy; Chattanooga Group, Chattanooga, TN, USA). Therapists received additional training and information on NMES by an experienced laryngologist certified to use surface electrical stimulation. The training was given according to the manual of the manufacturer, the VitalStim certification course (<http://www.vitalstim.com>).

Skin preparation and electrode placement will be in accordance with the manufacturer's instructions.

Channel 1 is horizontally immediately above thyroid notch. Channel 2 is parallel, below notch.

Having applied the electrodes, the amplitude of each channel of the stimulator will be increased and the subject will identify when they will be able just feel it. The amplitude will be then further increased until the subject will feel a 'grabbing sensation' which corresponded to muscular contraction. This will be the amplitude used for the therapy. This process will be repeated for the second channel of the stimulator. The typical electrical stimulus is at 80 Hz and at 300 microsec, and it will be adapted to avoid annoying stimulus to the patients.

During therapy, both channels will be active. In "sham" group the same electrodes will be positioned.

To maintain the double-blind study, the electrodes in the "sham" group will be placed in the same positions as the active treatment, with a current between 3 and 5 mA (average of 3.5 mA) until the patient begins to feel a slight tingling, current unable to perform muscle contraction. (Park J. S. et Al).

During electrical stimulation, traditional swallowing therapy will be carried out, by a trained speech therapist.

Before the study starting, the team of the 8 Centres, reached a consensus for the administration of clinical scales and how to score the FEES findings.

Briefly:

Subjects:

136 clinically definite MS subjects, both outpatients and inpatients (see inclusion and exclusion criteria below). Each patient will be informed on overall requirements of the study, and his/her written consent will be obtained

Primary Outcome:

The first aim of this study is to determine whether NMES adds benefit to a speech therapy traditional program. Performance between the groups will be compared at completion of treatment, after adjustment for baseline differences.

The mean difference at ASHA score between SRT-S vs SRT-NMES will represent the primary outcome.

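### The protocol's only repeated-measures model tests change within each arm up to T2; it cannot show added benefit of NMES, and no named model reaches the T0-T3 secondary outcomes

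*Protocol*

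**What the plan says.** The statistical text under Primary Outcome in the Protocol names two models for outcomes.

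- **First aim:** "will be used analysis of covariance comparing changes in study outcomes from baseline to T2", with adjustment for baseline measures. This agrees with the definition of the primary outcome: "Performance between the groups will be compared at completion of treatment, after adjustment for baseline differences", and "The mean difference at ASHA score between SRT-S vs SRT-NMES will represent the primary outcome".
- **Repeated measures:** "To evaluate the differences intra-group, we will performed longitudinal analyses using general linear models for repeated measures". The data for this model are "repeated measures of outcome data collected at baseline to T2".

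Three other statements bear on the point.

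- Inclusion criterion 5 in Materials and methods requires "ASHA<6 and DYMUS >2". ASHA is the primary outcome and DYMUS is the first secondary outcome listed.
- The visit schedule at the end of Materials and methods says "After 8 (T1) every patient will be examined using: ASHA scale", together with VAS and meal time. T2 has clinical and instrumental examinations. T3, 12 weeks after treatment ends, has clinical evaluations.
- "Secondary outcome will be the differences obtained at T0-T2 and T0-T3 in the two groups" is how the secondary outcomes are introduced.

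Rehabilitation treatment gives both arms 16 sessions of traditional dysphagia therapy.

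**The concern.** The trial asks whether NMES adds something to traditional therapy, which is a question about the difference between arms. The one model suited to several visits is assigned to a different contrast, change within each arm. That change contains the effect of the therapy common to both arms, the passage of time, placebo response and, where the qualifying score also serves as baseline, regression to the mean. A small p-value within the NMES arm therefore says nothing about NMES.

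Two such tests side by side also invite the reading that NMES worked because its arm was significant and the sham arm was not. That pattern can be common when both arms improve equally.

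Finally, the window of both models ends at T2, while the outcomes run to T3. The durability of any effect, a stated secondary question, has no model in this text.

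**Working it through.** **1. The plan's own figure.** The sample size reproduces. h = 2·asin(√0.6) − 2·asin(√0.3) = 0.6129, and n = 2·((1.960 + 1.282)/h)² = 55.95, hence 56 per arm. The point below does not change it.

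**2. Model against outcome, by visit.**

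| Visit | ASHA | Between-arm model named | Within-arm model named |
|---|---|---|---|
| T1 | measured | none | inside the window, not named |
| T2 | measured | ANCOVA | yes |
| T3 | clinical evaluation | none | outside the window |

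T2 is used between arms. T3 has a stated secondary outcome but no named model.

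**3. Within-arm change when NMES adds nothing, from the plan's own sham response.** The sample-size text expects 30% response under sham. As an illustration, take a response to be a gain of one ASHA level, with 56 patients and nobody else changing. The mean gain is 0.30, the SD is √(0.30 − 0.30²) = 0.458, and t ≈ 0.30/(0.458/√56) = 4.9. The sham arm would then almost surely be significant. If 10% lose one level, the mean is 0.20, the SD 0.60 and the chance of significance about 70%. If 20% do, it is about 19%.

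**4. Regression to the mean alone.** The Protocol gives no ASHA SD, mean or reliability, so these are assumptions: SD 1.3 before selection, scores rounded to 1-7, patients kept if below 6, no true change, and the qualifying score used as baseline. With 15% dropout, 136 × 0.85 / 2 = 57.8, so 58 per arm. The test is a paired t-test at two-sided 5%, counting improvement only (2.5% nominal).

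| Screening mean | Apparent gain in levels, reliability 0.9 to 0.7 | Chance of significant improvement in one arm |
|---|---|---|
| 5.5 | 0.16 to 0.36 | 40% to 76% |
| 5.0 | 0.11 to 0.26 | 23% to 47% |
| 4.5 | 0.07 to 0.17 | 12% to 24% |
| 4.0 | 0.05 to 0.11 | 7% to 12% |
| 3.5 | 0.03 to 0.06 | 5% to 6% |

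The effect is large when the source population sits near the cut-off and close to nil when few patients are excluded.

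**5. The primary analysis under the same mechanism.** In 2,000 simulated trials (56 per arm, worst half selected, reliability 0.8, no effect), the baseline-adjusted between-arm ANCOVA rejected in 4.45%, close to the nominal 5%.

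**6. Significant in NMES, not in sham, with equal improvement in both arms.** If p is the within-arm power, the chance is p(1 − p). With 58 per arm:

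| Common improvement (SD of change) | p | p(1 − p) |
|---|---|---|
| 0.2 | 0.32 | 22% |
| 0.3 | 0.61 | 24% |
| 0.4 | 0.85 | 13% |
| 0.5 | 0.96 | 3.6% |
| 0.6 | 0.99 | 0.6% |

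**The case against.** The strongest reply is that the efficacy test is already the right one. The first aim rests on a between-arm, baseline-adjusted comparison at T2, and the within-arm sentence is labelled as such. Nowhere does the Protocol base a conclusion about NMES on it or plan to compare one arm's p-value with the other's. Reporting change within arms beside a valid ANCOVA is common practice. All of this stands, and it limits the point to secondary analyses.

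A reader might infer more than the text supports, in three ways.

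- **That the within-arm model will show improvement without any effect.** It can. Step 4 gives 5% to 75%, depending on inputs the Protocol does not state. The Protocol also does not say whether the qualifying score is the T0 score.
- **That the repeated data go unused between arms.** T2 is exactly what the ANCOVA uses, and the T0-T3 differences in the two groups most naturally mean a between-arm comparison. T1 is a mid-treatment visit, and leaving it without a between-arm test is not an error in itself.
- **That discordant significance is frequent.** The 22% to 24% in step 6 is near the maximum of p(1 − p). It falls below 4% once the common improvement reaches 0.5 SD, which is plausible with active therapy in both arms.

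It may also be said that the method for T3 could be in a statistical analysis plan that is not shown. That is fair for the mere absence of a method. It does not answer the fact that this text fixes a contrast and a window for its longitudinal model, and that neither fits the question or the outcomes stated beside it.

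**Conclusion.** The point holds for the secondary analyses and is of minor to moderate weight. The Protocol fixes its only repeated-measures model on a contrast that cannot show added benefit of NMES, and both named models end at T2 although T0-T3 differences are secondary outcomes. That much rests on the text alone.

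The size of any spurious within-arm gain rests on the assumptions in step 4: about 5% to 75% for one arm of 58, against 2.5% nominal in that direction. The primary ANCOVA at T2 and the sample size are not affected.

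**What to change.** 1. Keep the baseline-adjusted ANCOVA at T2 as the primary analysis.
2. Replace the within-arm model with a between-arm repeated-measures model for each outcome, with arm, visit, arm × visit, baseline value and centre. Include the post-baseline visits at which the outcome is measured: T1, T2 and T3 for ASHA and VAS, and T2 and T3 for the other secondary outcomes where measured. Since T3 is described as clinical evaluation only, state which outcomes have a T3 value.
3. Report the arm difference with its confidence interval at T2 and T3.
4. Give within-arm changes descriptively, and state that no conclusion on efficacy is drawn from them.

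The cost is analysis wording. It needs no added visit or measurement and no change in sample size.
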